## **9.8 QUALITY CONTROL**

All programming will be quality controlled by two-step code checking. All results generated will be reviewed internally by two co-investigators separately prior to finalization.

## **9.9 LIMITATIONS OF THE RESEARCH METHODS**

Claims and EMR data are subject to certain limitations. The presence of a claim for a filled prescription or prescription absent a claim does not indicate that the medication was consumed or that it was taken as prescribed, and any medications filled over-the-counter or provided as samples by the physician will not be observed in the claims data. Finally, as with all claims-based analyses, study results may not be generalizable to the overall population as patients who have commercial health insurance may be different from those with non-commercial or without (commercial) health insurance. Database I underrepresents the population aged 65 years and older, which may affect external validity in the case of Medicare, Medicare Advantage or Medicaid patients. Since unmatched patients will be excluded, the results may not be generalizable to all patients. Some study measures and outcomes will include missing data and hence reduce the sample size. Not all patients in Database II will have lung function results or ACT scores, therefore, the sample size for related secondary endpoints or sub-group analyses may produce results for these analyses that are not generalizable. While duplication analyses will make double counting the same patient across both datasets negligible, it should be noted that the same patient may be present in both cohorts.

Including patients with persistent use of high-dose ICS/LABA (as opposed to an increase in ICS/LABA dose) in the NonTio group, may complicate the interpretation of the results, as patients with a deterioration in their asthma necessitating an increase in asthma medication (Tio group) will be matched to patients continuing on the same medication (high-dose ICS/LABA).

No claims regarding the effectiveness of Tio should be made on the basis of this study. This real-world evidence study lacks controls available with randomized controlled trials. Patient misclassification, missing data, objective and reliable measurement of patient outcomes, and lack of detailed information regarding subjects' clinical history or clinical status during the study timeframe may undermine the accuracy of our study results.

## **9.10 OTHER ASPECTS**

The IMS® PharMetrics Plus database is comprised of adjudicated claims for more than 150 million unique enrollees across the US. Enrollees with both medical and pharmacy coverage in 2012 represented 40 million active lives. Patients in the majority of three-digit zip codes and in every metropolitan statistical area of the US are represented, with coverage of data from 90% of US hospitals, 80% of all US doctors, and representation from 85% of the Fortune 100 companies. Because the database is constructed from a variety of geographic regions and employer groups, the database maintains a level of diversity while representing the overall trend in commercial health plan coverage. The underrepresentation of the population aged 65 years and older may affect external validity in the case of Medicare, Medicare Advantage or Medicaid patients.

EMRClaims+®, will offer lung function results, Asthma Control Test (ACT) scores, as well as eosinophil counts for asthma patients in addition to administrative data. EMRClaims+® is an integrated health services database containing more than 20 million EMR across 7 states in the Midwestern region of the United States. The database includes administrative insurance claims across approximately 690,000 lives linked to an overlapping healthcare provider database of EMR, including laboratory values, and provider billing files. This data source uniquely provides a strong-level of internal validity since two separate sources (EMR and administrative data) cross reference unique patient identifiers. In the event of discrepancies between administrative files and EMR data (or for uncertainty about disease classification), manual evaluation of the individual patients' medical records is conducted to provide resolution based on access to the complete patient medical history in the EMR.

The databases do not have the capability to uniquely identify members who disenroll and re-enroll; consequently, these individuals are assigned a new identifier and may be represented in the data as two unique subjects. It is also possible that a patient may be in both cohorts. Both possibilities will be checked using zip codes. If two patients are suspected of being the same, only the data with the longer follow-up period will be used.

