### **9.1 STUDY DESIGN**

Data extraction from both databases (I and II, see [section 9.4](#)) will be conducted by

. All patients will be required to have a prescription for ICS/LABA therapy [e.g. Advair (Diskus and HFA), Airduo, Breo, Dulera, or Symbicort]. The date of the first prescription of ICS/LABA within the study period (Jan 1st 2016 to Nov 30th 2018) will be defined as ICS/LABA-initiation (ICS/LABAi) date. This baseline cohort will then be followed to identify two cohorts (two arms of the study). One cohort that receives a prescription for Tiotropium Respimat® 1.25 mcg (on top of baseline ICS/LABA) will be classified as the ‘Tio’ group, and the second cohort that receives a “step-up” from baseline low-dose ICS/LABA to medium/high dose ICS/LABA or from baseline medium dose ICS/LABA to high dose ICS/LABA or an additional prescription/refill of high-dose-ICS/LABA following the first prescription of baseline high dose ICS/LABA within the study period, will be classified as the ‘NonTio’ group. The date of the first prescription for Tiotropium Respimat® 1.25 mcg in the ‘Tio’ group will be defined as the index date for the ‘Tio’ group. Similarly the date of the first prescription for a “step-up” from baseline low-dose ICS/LABA to medium/high dose ICS/LABA or from baseline medium dose ICS/LABA to high dose ICS/LABA or an additional prescription/refill of high-dose-ICS/LABA following the first prescription of baseline high dose ICS/LABA (evidenced by at least 90-days of prescription utilization) within the study period will be defined as the index date for the ‘NonTio’ group.

Patients will be required to have a minimum follow-up period of 30 days after the index date for the analyses of the primary endpoint with no limit on the maximum period (this 30-day minimum follow-up period requirement will be waived in a sensitivity analysis). Subject to sample size requirements, patients will be required to have available records for at least 12 months prior to the index date to ensure no prior use of Tiotropium Respimat® and to establish baseline patient characteristics. This 12-month period prior to the index date will be defined as the pre-index period.

Figure 9.1.1 Study Design

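### Suspected duplicates are resolved by length of follow-up, so the analysed record, its index date and sometimes its treatment group are chosen on post-index information

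*Combined protocol and SAP*

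**What the plan says.** Section 9.10 describes two ways in which one person can enter the data twice. Members who leave and rejoin a plan cannot be recognised: "these individuals are assigned a new identifier and may be represented in the data as two unique subjects". In addition, "It is also possible that a patient may be in both cohorts". Detection is given in one sentence: "Both possibilities will be checked using zip codes". Resolution is given in the next: "If two patients are suspected of being the same, only the data with the longer follow-up period will be used".

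Section 9.9 expects double counting across the two datasets to be negligible once duplication has been examined, but adds that "it should be noted that the same patient may be present in both cohorts".

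Section 9.1 measures follow-up from the index date, requiring a "minimum follow-up period of 30 days after the index date for the analyses of the primary endpoint with no limit on the maximum period". It also wants 12 months of records before index so that earlier tiotropium use can be ruled out. Section 9.11 allows 6 months if the sample would suffer.

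No section gives a tie-break, a rule for two records that fall in different arms, or the order of de-duplication and matching.

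**The concern.** A cohort study should fix who is in it, from what date and in which group, using information available at that date. Here, how long a person was later observed decides these things whenever two records are thought to belong to one person. The choice brings with it the index date, the baseline covariates used in the propensity score and, if the records differ in exposure, the arm.

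Two consequences follow. If observation tends to end for reasons connected with exacerbation, the rule favours records with fewer events. And if the kept record is the later one, tiotropium use seen only under the earlier identifier is lost to view, which defeats the purpose of the no-prior-use check in section 9.1.

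The plan treats a related form of conditioning on follow-up as worth testing: "this 30-day minimum follow-up period requirement will be waived in a sensitivity analysis". The duplicate rule has no such check.

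**Working it through.** The plan gives no figure for duplicates, so there is none to reproduce on this point. The steps below ask whether the rule uses post-index information, whether it favours one arm, and how much it could matter.

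**1. Timing.** Follow-up starts at index (9.1) and the longer follow-up is kept (9.10). The selecting variable is therefore known only after index. If both records end on the same date, longer follow-up simply means earlier index, and the rule does no harm. It matters when the end dates differ.

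**2. Can the arm change?** Section 9.1 uses the word cohort for the arms ("This baseline cohort will then be followed to identify two cohorts (two arms of the study"), while section 9.12 uses Cohort I and II for the databases. If 9.10 means arms, a change of arm follows directly. If it means databases, it still arises when a person's two records qualify for different arms.

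**3. Which record is longer?** Take two enrolment spells with follow-up F1 and F2. The study period, January 2016 to November 2018, is 12 + 12 + 11 = 35 months. Assume that follow-up stops at its end. The second record needs 12 months before its index under the new identifier, so F1 + gap + 12 + F2 ≤ 35, giving F1 + F2 ≤ 23 months (29 with the 6-month fallback). Within that limit either can be the longer, so the documents fix no direction.

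**4. Size, by simulation.** All inputs are assumed: true rate ratio 1, baseline rate 0.02 per month, frailty variance 1, follow-up of 1 month plus an exponential time with mean 12 months, event rates over the first 6 months, 3,000,000 people. Each duplicate has one Tio and one NonTio record. The comparator is a random choice of record, standing for any choice unrelated to outcome. Monte Carlo error is about 0.005. Entries are Tio/NonTio rate ratios.

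| Follow-up ends soon after an exacerbation | Choice of record | 1% duplicates | 5% | 10% |
|---|---|---|---|---|
| Unrelated | Longer | 1.005 | 0.998 | 0.999 |
| Unrelated | Random | 0.998 | 0.999 | 1.005 |
| 30% in both arms | Longer | 1.000 | 0.989 | 0.992 |
| 30% in both arms | Random | 0.999 | 0.996 | 0.994 |
| 50% Tio, 10% NonTio | Longer | 0.997 | 0.979 | 0.955 |
| 50% Tio, 10% NonTio | Random | 1.000 | 0.997 | 1.000 |

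Only the last pattern shows a clear shift, and its 50% and 10% have no source in the plan.

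**5. Power is not the issue.** Using the section 9.5 scenario based on the 48-week trial, with two-sided alpha 0.05 assumed:
- Events: 4,200(1 − e^(−0.028×11)) + 2,100(1 − e^(−0.0224×11)) = 1,113.4 + 458.6 = 1,572.
- Power: Φ(√(1,572 × 2/9) × |ln 0.8| − 1.96) = Φ(2.21) = 98.6%, against the stated 98%.
- With 10% fewer events (1,414.8): Φ(2.00) = 97.7%.

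The other scenario gives 53.2% at its quoted 5.5 months, not 77%. That is a separate matter. There, 10% fewer events gives 49.0%.

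**6. Zip code as a screen.** Chance same-zip pairs among n = 6,300 people in K equal areas number n(n − 1)/(2K). The number of areas is assumed: about 19,800 for K = 1,000, 3,970 for 5,000 and 660 for 30,000. Zip code can only be a first screen, and the plan does not name what follows it.

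**The case against.** The strongest reply is that no material bias has been shown. That largely stands. The lookback and the 30-day minimum limit how many people can have two eligible records. Overlapping records in the two databases would usually place a person in the same arm. The simulation moves clearly only under an extreme assumed difference between arms, and at 1% duplicates it is within Monte Carlo error of 1.

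A reader might infer that the rule systematically discards Tio records, because an earlier NonTio spell would have the longer follow-up. The documents do not support this: an earlier spell is cut off by disenrolment, and either record can be the longer. Nor would an earliest-index rule protect Tio. A person who is NonTio first and Tio later would always be counted as NonTio.

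A reader might also infer that everyone sharing a zip code is treated as one person. The text speaks of suspicion and of duplication analyses, and the chance-pair counts make that reading implausible. What stands is that the further linkage fields are unstated.

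On prior tiotropium, if the check is read strictly as a 12-month window, a person with two separate spells could satisfy its letter. The aim of excluding earlier users would still be missed.

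**Conclusion.** The point holds as a small design flaw. A stated rule lets post-index observation time choose the record, index date, baseline and, for discordant pairs, the arm, and nothing elsewhere in the plan corrects it. Bias in the hazard ratio requires follow-up length to be related to outcome. In the simulation the shift was clear only when that relation differed by arm. Its size cannot be computed from the documents because the number of duplicates and of discordant-arm pairs is not given. It is probably small, and its direction is open: the simulated values below 1 reflect the assumed pattern and are not a prediction for this study. The case for changing the rule is that a choice fixed at index costs almost nothing and removes the question.

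**What to change.** Replace the resolution rule in section 9.10 with: keep the record with the earliest qualifying index date and assign the group from that index, regardless of follow-up length. This fits the first-prescription index in section 9.1 and keeps earlier tiotropium use in view.

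- **Order.** Apply it before propensity score matching. Section 9.12 matches each database separately, so removing a cross-database duplicate later would break matched sets.
- **Detection.** Flag on zip code plus sex and age, which Table 1 lists for both databases (age in 10-year increments; birth year is not named). Add matching fill or visit dates only for records that overlap in time, such as one person in both databases. Separate enrolment spells have no common dates.
- **Reporting.** Give the duplicates removed and the discordant-arm pairs, by group.
- **Consistency.** The abstract places anyone prescribed tiotropium in Tio and the rest in NonTio. Confirm that a single identifier meeting both definitions is handled in the same way as a duplicate pair.

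The cost is two or three sentences and a small program change. Some kept records will have shorter follow-up, and people who are NonTio first and Tio later count as NonTio, which may lose a few Tio records.

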## 9.11 SUBJECTS

1. Patients with least one asthma diagnosis in the inpatient setting or at least two separate instances of asthma diagnosis (separated by at least 30 days) recorded in the outpatient or emergency room setting will be included (ICD 9 CM: 493.xx or ICD 10: J45-J45.999).
2. Patients will be required to be already on ICS/LABA.
3. Patients below the age of 6 years on the ICS/LABAI date will be excluded.
4. Patients will be required to have available records 12 months prior to the index date (6 months will be used if patient exclusions due to this criteria adversely affect the study sample size).
5. Patients with a diagnosis of COPD at any time during the study period will be excluded.
6. Those who are on biologics at baseline will be removed.
7. After the PSM process, unmatched patients will be excluded.

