### 9.3.2 Outcomes

#### 9.3.2.1 Primary outcomes

*(Database I/II combined)*

The primary outcome measure is time to first exacerbation per person. Exacerbations will be defined as either a hospitalization with a primary diagnosis of asthma, an ER visit with a primary diagnosis of asthma, an asthma exacerbation diagnosis recorded (ICD 493.02, 493.12, 493.22, 493.92, J45.21, J45.31, J45.41, J45.51, J45.901). The primary endpoint analysis will be of patients aged 12 years and above.

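### The qualifying asthma diagnoses are not dated relative to index, so a post-index asthma hospitalization can both admit a patient and count as the primary event

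*Combined protocol and SAP*

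**What the plan says.** Section 9.11, item 1 gives two routes into the study: "Patients with least one asthma diagnosis in the inpatient setting or at least two separate instances of asthma diagnosis". One inpatient asthma diagnosis is enough. Otherwise the patient needs two diagnoses, "separated by at least 30 days) recorded in the outpatient or emergency room setting will be included". The 30-day gap is between the two diagnoses and is the only timing condition in the item. The qualifying codes are "ICD 9 CM: 493.xx or ICD 10: J45-J45.999".

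Section 9.3.2.1 builds the primary outcome from the same kinds of record: "Exacerbations will be defined as either a hospitalization with a primary diagnosis of asthma, an ER visit with a primary diagnosis of asthma", or one of a list of exacerbation codes running from 493.02 to J45.901.

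Two other rules look back from index. Section 9.11, item 4 says "Patients will be required to have available records 12 months prior to the index date" (6 months as a fallback), and section 9.1 gives the purpose of that look-back as "to ensure no prior use of Tiotropium Respimat® and to establish baseline patient characteristics". Section 9.11, item 2 says "Patients will be required to be already on ICS/LABA". Neither says when asthma must have been diagnosed.

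**The concern.** An eligibility rule for a cohort followed from an index date should be decidable on that date. Item 1 is not: whether some patients belong to the cohort depends on what happens to them after index, and one thing that can decide it is the primary event.

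A patient without a qualifying diagnosis before index who is later hospitalized for asthma enters with an event already assured. An otherwise similar patient who has neither an event nor enough routine asthma visits never enters. That is selection on the outcome. It raises event rates in whichever group it affects, and it distorts the Tio versus NonTio comparison if it affects the groups unequally.

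**Working it through.** **Does the text allow it?**

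- *Date limit.* Items 3 to 6 of section 9.11 each carry a time reference: age at ICS/LABA initiation, records before index, COPD over the whole study period, biologics at baseline. Item 1 has none.
- *Code overlap.* Every exacerbation code listed in section 9.3.2.1 lies inside the 493.xx and J45 to J45.999 ranges of item 1.
- *Inpatient route.* A first post-index hospitalization with asthma as primary diagnosis meets item 1 alone and is a primary event.
- *Outpatient/ER route.* A post-index ER visit or coded outpatient exacerbation is not sufficient alone. It can be one of the two diagnoses, with the other at least 30 days away.
- *Does anything else close the gap?* The 12-month rule asks for available records, not for an asthma code in them. Table 1 does not match on having a pre-index asthma diagnosis. A patient with no asthma code and no OCS before index would be classed as well controlled, and the further matching on asthma-related admissions and visits applies only to patients who are not well controlled. Sections 9.9 and 9.12 do not mention the issue.

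**How large could it be?** The plan states no figure for this. Its event risks, from section 9.5, are 6.4% over 5.5 months and 26.9% over 11 months. They imply monthly hazards of −ln(1 − 0.064)/5.5 = 0.0120 and −ln(1 − 0.269)/11 = 0.0285, against the stated 0.012 and 0.028.

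*Illustration 1, true HR 1.00.* Let u be the share of a group that entered only through a post-index event; all of these patients have the event. Observed risk = (1 − u)·p + u, and apparent HR = ln(1 − risk in Tio)/ln(1 − risk in NonTio), treating hazards as constant. Take u = 1% in NonTio and 0% in Tio (assumed).

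- p = 6.4%: NonTio risk = 0.99 × 0.064 + 0.01 = 0.0734. HR = ln(0.9360)/ln(0.9266) = 0.868.
- p = 26.9%: NonTio risk = 0.99 × 0.269 + 0.01 = 0.2763. HR = ln(0.7310)/ln(0.7237) = 0.969.
- Reverse imbalance: 1/0.868 = 1.15 and 1/0.969 = 1.03.

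A 1% share is less modest than it looks. If q is the share of candidates with no qualifying pre-index diagnosis, and they enter only by having an event, then u = qp/((1 − q) + qp). Solving for u = 1% gives q = 0.01/0.0734 = 13.6% of NonTio candidates at 6.4% risk, or 0.01/0.2763 = 3.6% at 26.9% risk, against none in Tio.

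*Illustration 2, true HR 0.80.* Use the hazards of section 9.5 (0.012 and 0.0096; 0.028 and 0.0224 per month) and the same entry rule, so that observed risk = p/((1 − q) + qp). All values of q are assumed.

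| q NonTio / q Tio | HR, 5.5 months | HR, 11 months |
|---|---|---|
| 0% / 0% | 0.800 | 0.800 |
| 10% / 10% | 0.801 | 0.802 |
| 20% / 20% | 0.801 | 0.805 |
| 20% / 10% | 0.715 | 0.726 |
| 10% / 20% | 0.897 | 0.889 |

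Equal values of q leave the HR at about 0.80 but raise observed risk: NonTio goes from 6.4% to 7.1% or 7.9% at 5.5 months, and from 26.5% to 28.6% or 31.1% at 11 months. Unequal values move the HR in either direction.

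**The case against.** The strongest reply is that the plan is silent, which is not the same as permitting diagnoses from any date. The objective and abstract describe patients who have asthma and are then followed, asthma control is a baseline variable, and where the authors wanted an unrestricted window, as for COPD, they said so. The study design figure (Figure 9.1.1) is not shown in the text available and may mark a window. Patients already on ICS/LABA with a year of records will often have earlier asthma codes, and in Database II uncertain disease classification is resolved by record review. So the affected group may be small.

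These points limit the likely size but do not supply a date. The COPD rule cuts both ways, since it shows that this plan does select on diagnoses made after index. A window marked in a figure should still be stated in the eligibility text.

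A reader might go further in three ways that the documents do not support.

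- *That any post-index ER visit admits a patient.* It does so only when paired with a second diagnosis at least 30 days away.
- *That every comparable event-free patient is left out.* The outpatient route accepts any asthma code, so routine visits after index can also qualify an event-free patient. Both illustrations ignore this and so overstate the effect for given values of q.
- *That the group observed longer has more chance to qualify late, which would give the bias a direction.* No follow-up by group is given, and both groups have the same 30-day minimum with no maximum.

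**Conclusion.** The point holds as a gap in the eligibility rule. Followed as written, item 1 allows selection on the primary outcome, and matching on the Table 1 variables does not remove it.

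Its size and direction are unknown, because the documents do not give the share of patients who qualify only after index, in total or by group. A reader might take the HRs of 0.87 and 0.97 as an estimate of bias in favour of Tio. They are not: they rest wholly on an assumed 1% versus 0% imbalance, the reverse imbalance gives 1.15 and 1.03, and similar values of q in the two groups leave the HR nearly unchanged. They show only that a small imbalance in event-qualified patients could matter beside the HR of 0.80 used for power, more so at the lower event risk. The change should be made because it is cheap and removes the problem by design, not because a bias has been demonstrated.

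**What to change.** Amend section 9.11, item 1 so that the inpatient diagnosis, or both outpatient/ER diagnoses, must be recorded on or before the index date. Use all available records up to index rather than a fixed 12 months, so that the rule also works under the 6-month fallback in item 4. Report the number removed by this condition, by group, in the attrition table already planned in section 9.7.1. If Figure 9.1.1 shows a diagnosis window, make the text and the figure agree.

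The cost is one clause and the loss of patients whose asthma is coded only after index. That loss is likely small, but the documents do not quantify it; the attrition table would.

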## **9.4 DATA SOURCES**

Two separate databases will be appended to create the analytic dataset to obtain sufficient power for the primary endpoint analysis. This approach will provide both comprehensive geographic representation from national claims, and important asthma clinical measures available through electronic medical records (EMR). Both databases have been widely published in the academic asthma literature.

As a general note, this study protocol attempts to anticipate availability of detailed data elements of the two real-world data sets listed below. Consistent with accepted research standards using retrospective administrative data, evaluation of missing data and study variables is often required to ultimately finalize the study protocol as it relates to inclusion of covariates as well as secondary outcome measures.

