## **9.5 STUDY SIZE**

The expected number of asthma patients aged 12 years and above, without concurrent COPD, and continuous enrollment for 12 months prior to the Tiotropium Respimat® date is estimated to be approximately 2,100 to be matched to double (4200 patients) the number of NonTio patients resulting in a total N =6,300. Power calculation was conducted for the primary endpoint, time-to-first exacerbation by the end of the follow-up time. The calculation was based on detecting a significant treatment effect using Cox proportional hazard model. Estimates were obtained from the MEZZO trial comparing tiotropium 2.5 µg vs. salmeterol ([P15-01655](#)). Assuming 6.4% of patients in the control group followed

up for 5.5 months will have an exacerbation (based on the salmeterol group in the MEZZO study) and assuming a constant hazard rate, equating to an exponential rate parameter of 0.012 per month for the control group and 0.0096 per month for the Tio group, the power is calculated to be 77%. Using the Primo study, assuming 26.9% of patients in the control group followed up for 11 months will have an exacerbation (based on the Tio R 5 group in the 48-week study Primo) and assuming a constant hazard rate, equates to an exponential rate parameter of 0.028 per month in the control group and 0.0224 per month in the Tio group, the power is 98%. The Mezzo-derived power calculation likely underestimates the power since our study design includes sicker patients that required a step-up in ICS treatment (not required in the Mezzo Study). While we expect that the actual power will lie between the two estimates (assuming that the patient population is similar to the less severe Primo patients and the more severe MEZZO patients), the estimated power is greater than 77%.

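### Does the option to cut the look-back from 12 to 6 months need a numerical trigger in the plan?

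*Combined protocol and SAP*

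**What the plan says.** Section 9.1 makes the look-back conditional: "Subject to sample size requirements, patients will be required to have available records for at least 12 months prior to the index date". It then gives the window a single definition: "This 12-month period prior to the index date will be defined as the pre-index period". Section 9.11, item 4, supplies the alternative: "6 months will be used if patient exclusions due to this criteria adversely affect the study sample size".

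The only section that deals with numbers of patients is 9.5. There the count of eligible patients aged 12 and over with "continuous enrollment for 12 months prior to the Tiotropium Respimat® date is estimated to be approximately 2,100". These are to be matched 1:2, for a total of 6,300. Power for time to first exacerbation is given as 77% on rates taken from MEZZO and 98% on rates taken from Primo, and the authors say "we expect that the actual power will lie between the two estimates". Section 9.5 does not state alpha, the study follow-up behind these figures, a target power or a minimum number of patients or events.

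**The concern.** The eligibility rule refers to a sample size requirement, and section 9.5 gives an expectation instead of a requirement. The study is retrospective, so the outcomes already exist when the look-back is chosen. A choice between two cohorts that is not tied to a number or a time could, in principle, be made with results in view.

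The look-back also does real work. It screens out earlier tiotropium use and supplies the comorbidities, admissions, ER visits and oral steroid use that go into the propensity score. Section 9.12 relies on that matching to limit channelling, and halving the window thins the information.

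Section 9.5 seems unable to settle the matter, because its two scenarios react very differently to the same loss of patients. It also describes the study population as "similar to the less severe Primo patients and the more severe MEZZO patients", although the MEZZO rate is the lower of the two, which blurs which scenario governs.

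**Working it through.** **Inputs.** All come from section 9.5 except where marked.
- Monthly rates, control and Tio: 0.012 and 0.0096 (MEZZO); 0.028 and 0.0224 (Primo). The hazard ratio is 0.0096/0.012 = 0.0224/0.028 = 0.80, and |ln 0.80| = 0.2231.
- 2,100 Tio and 4,200 NonTio, so the allocation factor is (1/3)(2/3) = 2/9.
- Assumed: two-sided alpha 0.05 and one common follow-up T for all patients.

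**Step 1: reproduce the plan's power.** Expected events are D = 4,200(1 − e^(−λc·T)) + 2,100(1 − e^(−λt·T)). By Schoenfeld's formula, power = Φ(√(D × 2/9) × 0.2231 − 1.96).

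Solving for the T that gives 77% on the MEZZO rates yields T = 9.86 months:
- MEZZO: D = 658; √(658 × 2/9) × 0.2231 − 1.96 = 0.739; power 77%.
- Primo at the same T: D ≈ 1,429; √(1,429 × 2/9) × 0.2231 − 1.96 ≈ 2.02; power 97.8%, against the stated 98%.

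One follow-up explains both figures. With an unpooled variance, T becomes 10.73 months and the Primo power is again 97.8%. A study follow-up of 5.5 months would give only about 53% on the MEZZO rates (Schoenfeld). The 5.5 months is therefore best read as the period from which the rate was derived: −ln(1 − 0.064)/5.5 = 0.012.

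**Step 2: what a shortfall would cost.** With T held at 9.86 months and 1:2 matching:

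| Matched Tio | Power, MEZZO rates | Power, Primo rates |
|---|---|---|
| 2,100 | 77% | 98% |
| 1,800 | 71% | 96% |
| 1,500 | 63% | 92% |
| 1,200 | 53% | 85% |

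Keeping 77% needs 2,100 Tio on the MEZZO rates and 658/(1,429/2,100) = 967 on the Primo rates. The first number is 2,100 by construction, because T was solved to make it so. The second asks for 77% in a scenario where the plan reports 98%. The contrast shows how power depends on the event rate. It does not reveal two competing requirements in the plan.

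**Step 3: could a trigger be written that works?** An event trigger depends on the formula: 658 by Schoenfeld, about 713 with the unpooled variance at its own follow-up. It also cannot be checked before outcomes are tabulated, which is the moment the safeguard is meant to protect. A patient-count trigger can be checked in time. But setting it at 2,100 would invoke the fallback on the loss of one expected patient, and any lower value depends on a follow-up that is seen only once the data are in hand.

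**The case for a change.** The strongest argument for a change is that disclosing an option is not the same as stating a rule. The plan does not say when the choice is made or whether it may differ between the two databases, which are matched separately. Section 9.4 allows the protocol to be finalised after a look at the data, but only for covariates and secondary outcomes, so eligibility for the primary cohort is not covered. A sentence on timing would cost little.

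The omission stands as a fact. Its consequence is limited for these reasons:

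- The natural reading of item 4 in section 9.11 is that 6 months replaces 12 for everyone, and that the sample size meant is the one in section 9.5. That section says the MEZZO-based figure probably understates power, so the lower rate is the cautious benchmark.
- A switch made on counts alone does not inflate type I error. Counts are also what an analyst would have first: section 9.7.1 promises attrition at each step, a comparison of baseline measures before and after matching, and adjustment for whatever stays unbalanced. A switch would be visible.
- Section 9.4 of the protocol extracts Database I from January 2015 for follow-up from January 2016, so a year of earlier calendar time is built in there.
- The history lost with a 6-month window cannot be sized from the documents. The rates in section 9.5 are first-exacerbation rates from trials, while Table 1 matches on control status, resource use, oral steroids, comorbidity and dose. Events may also cluster near the index date, since that date marks a treatment change for many patients. If section 9.12 is right that Tio patients have the worse history, the unmeasured part would count against Tio.

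The severity labels for Primo and MEZZO look transposed: the preceding sentence in section 9.5 says this study's patients are sicker than those in MEZZO. That is a clerical slip, and no rate or power figure depends on it.

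**Conclusion.** No change is called for. The plan discloses a contingency without a threshold, and analysts would ordinarily settle it from matched patient counts before opening the outcomes. The 77% and 98% are sound, given two-sided 0.05 and a common follow-up of about 10 to 11 months, neither of which is stated in section 9.5. The expected 2,100 already meets the 12-month rule, so the planned size does not depend on the fallback.

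If matching did fall short, the power at stake is as tabulated: at 1,500 Tio, for example, 63% or 92% depending on the event rate. Whether to recover some of that by accepting a shorter covariate window is a fair trade-off. The sponsor's preference for power is open, since section 9.4 says "Two separate databases will be appended to create the analytic dataset to obtain sufficient power for the primary endpoint analysis". Fixing 12 months would be defensible too, but it would give up that reserve and correct no error.
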